2.3. Benefit/Risk Assessment

The risk-benefit profile of phenserine is supported by nonclinical and clinical data from its early development as a cholinesterase inhibitor for the treatment of AD. In total, phenserine has been evaluated in 11 clinical trials, including initial safety and tolerability studies that included PK and PD assessments at different dose regimes (5mg, 10mg, 15mg) (6) in fed and fasted healthy normal subjects. In addition, phenserine's safety and efficacy profile for the treatment of AD were evaluated in eight Phase 2-3 randomized controlled trials (all of which were conducted entirely in the Europe) that enrolled 1,344 people with mild to moderate AD, including 645 participants who received phenserine for 6- to 12-months treatment duration. Although these clinical trials failed to show efficacy, design and methodological issues were identified by the company and subsequently verified by independent assessors as having confounded the analyses, the outcomes, and the conclusions. All available clinical data from these and other studies of phenserine are further described in the IB. These included subtherapeutic total daily doses, as evidenced by the drug's efficacy *and* safety profile. Importantly, the safety data from the completed trials support additional well-designed studies to better identify efficacious doses and evaluate potential disease-modifying effects in people with early or mild AD symptoms.

In addition to the reported clinical data, a standard package of nonclinical safety studies was performed to support the clinical program as it advanced. Completed studies include Good Laboratory Practice (GLP) 12-week subchronic studies in rats and dogs as well as chronic toxicity studies of up to 52 weeks treatment duration in rats, dogs and non-human primates and a carcinogenicity study in p53+ mice. Although the reports for the completed clinical and nonclinical studies are not all publicly available, the data were reviewed by relevant health authorities prior to allowing chronic studies in humans to proceed. All studies for which data are publicly available are summarized in the Investigator's Brochure. The risks and potential benefits of phenserine expected in this study are further summarized below based on publicly available information. In addition, more detailed information about phenserine's pharmacology and safety is detailed in the Investigator's Brochure (IB).

2.3.1. Risk Assessment

Several elements are included in the protocol to ensure safety of participants. Medical conditions or drugs with clinically important interaction with cholinesterase inhibitors are listed in the Exclusion criteria. In addition, frequent (bi-weekly) clinical and laboratory safety assessments are conducted. Specific conditions and changes needing particular attention are listed, including stopping criteria for changes in liver and kidney function tests.

In the 13-week GLP study in male and female rats, the effects of phenserine were evaluated in a at doses of 0, 5, 10, and 15 mg/kg/day (10 males and females per dose group). Evidence of cholinergic stimulation was observed at all dose levels and included tremors, increased salivation, staining around the mouth and excessive lacrimation. Clinical toxicity included decreased food consumption and decreased weight gain in the two high-dose groups. No consistent changes were observed in hematologic or clinical chemistry evaluations. Urinalyses showed a dose-related trend in decreased urine volume, increased specific gravity, decreased pH, ketonuria and albuminuria. These findings were considered secondary to decreased food

consumption and decreased weight gain. Macroscopic and microscopic examinations of body tissues postmortem showed only isolated findings, and no findings were considered drug related. In the 13-week GLP dog study, phenserine was administered once-daily to 8 animals per dose group (4 male, 4 female). All animals survived the study. Clinical signs of pharmacologic effect, including excessive salivation and tremors, were observed in animals receiving 1.5 or 5 mg/kg/day. There were no significant differences in body weight or food consumption at any dose level. In addition, no significant or drug-related findings were observed following fundoscopic ophthalmic examinations; electrocardiographic evaluations; hematologic, blood chemistry, and urinalysis measures; and macroscopic and microscopic examinations of all animals.

In another 1-Month Oral Dose Rat Study, with dose regimen: once daily oral doses of 0, 5, 10, 15, 20 and 25 mg/kg/day in 5 male rats per group, The most prominent cholinergic adverse effect was hypersalivation, which peaked within 1 hour of dosing and rapidly declined thereafter. There was a small reduction in food consumption seen at 5mg/kg which could be indicative of nausea. In the 3 highest dose groups 3 rats died (1 each at 15, 20, and 25 mg/kg). No consistent changes were observed in hematology or clinical chemistry parameters at termination. Gross examination of body tissues obtained postmortem showed only isolated findings, and there was no evidence of any drug effects (The 5mg/Kg dose is equivalent to 55-60mg in humans)

NIA (National Institute on Aging) and/or Axonyx (a biopharmaceutical company focused on the development of treatments for Alzheimer's disease) also conducted a standard panel of genotoxicity and safety pharmacology studies of phenserine to support clinical trials in the US and Europe.

Limited information regarding the metabolism of phenserine is in the public domain, but in Grieg et al., 2005, it is indicated that phenserine's metabolism principally involves N-demethylation and hydroxylation, and is mediated predominantly through the CYP3A4 pathway.

In early clinical pharmacology studies conducted in normal healthy volunteers, phenserine was shown to be rapidly absorbed and eliminated, and plasma drug concentrations correlated with erythrocyte AChE inhibition. Similarly, in studies that evaluated male and female elderly but otherwise healthy volunteers single doses of phenserine were well tolerated up to 10 mg. In the 20-mg group, dose-limiting side effects associated with cholinesterase inhibition included nausea and vomiting. No clinically significant changes in vital signs or clinical laboratory assessments were observed.

Phenserine showed high and predictable oral bioavailability across the dose levels. Over the 4-fold increase in dose, AUC₀₋₂₄ values increased by ~25%. T_{max} values ranged from 1.25-1.54 hr, and t_{1/2 elim} = 6.53 hr. Erythrocyte AChE inhibition reached peak values of 12%, 23% and 46% at 2 hours postdose for the 10, 15, and 20 mg/kg dose groups, respectively, and showed a linear relationship to phenserine plasma concentrations. Other studies have demonstrated that phenserine's effects on cognition and other neuropsychiatric assessments are positively correlated with increased CSF Aβ₄₀ and sAβPP levels as well as improved regional cerebral blood flow (rCBF) and metabolic rate for glucose (rCMRglc). In addition, CSF Aβ₄₂ levels, the Aβ₄₂/40 ratio, P-tau, and T-tau correlated negatively with rCMRglc and cognition (7,8).

In a follow-on study (5) elderly but otherwise healthy volunteers were randomized to receive once daily doses of phenserine immediate release capsules at 5 mg QD, 5 mg BID, 10 mg QD, or 10 mg BID (8 subjects/group) for 6 days. There were no dose-limiting or serious adverse events (AEs) reported for any subject. In addition, there were no clinically significant findings in clinical laboratory measures or ECG assessments across all dose groups. Peak plasma concentrations increased with dose but were similar across the QD and BID dosage regimens for each dose level. In addition, AUC₀₋₂₄ values remained consistent over the 6-day treatment period confirming that drug accumulation does not occur with repeated dosing. Erythrocyte AChE inhibition of 15% and 30% were observed for the 5 and 10 mg dose groups, respectively, regardless of the once- or twice-daily dosing schedules.

A subsequent NIA-sponsored Phase 2, 12-week RCT in 72 patients indicated that phenserine (10-15 mg b.i.d.) conferred significant improvements in cognitive function and a trend towards improvement in global outcome in people receiving the higher dose, with Cohen's D effect sizes of 0.3-0.4 for symptomatic benefits (6).

A second smaller RCT randomized 20 AD- patients equally to phenserine or placebo for 3 months. The placebo group then received donepezil after 12 weeks in an open design. Participants receiving phenserine had significantly greater improvements in cognition and improvements in cerebral glucose metabolism compared to the group treated with placebo, and the cognitive benefits were maintained after 6 months compared to the group receiving donepezil for the second 3 months of the trial (8).

Although these data are encouraging, the compound has not been assessed in people with early or mild AD, and the potential for disease modification has not previously been evaluated in human clinical trials.

From a safety perspective, in the larger trial with 72 participants, 77% of patients completed the study protocol. The overall discontinuation rate for the 15 mg twice daily group (23.6%) was only slightly higher than for the placebo group (17.1%). Withdrawals due to adverse events were slightly lower in the 15 mg twice daily group (5.9%) than in the placebo group (6.1%). Nausea (9% 10mg bd, 19% 15mg bd) and vomiting (5% at 10mg bd and 11% at 15mg bd) were the most common AEs in the active drug treated groups but did not contribute to dropouts and are comparable to rates for licensed cholinesterase inhibitors (3).

In a further single escalating dose safety study, 32 healthy elderly volunteers received single oral doses of phenserine tartrate up to 20 mg(5). Physical and vital signs were monitored over the ensuing 24 hours. Analyses were performed on plasma samples to determine PK, and PD effects were assessed as a function of AChE levels. No serious adverse events (SAEs) occurred; the most common AEs were headache and vomiting. Evaluation of PK/PD relationships suggested a linear correlation between plasma phenserine concentration and AChE inhibition. Other phase 1 studies indicated that the peak AChE effect occurs 30 minutes after dosing, with a maximum AChE inhibition of about 30% with a 10 mg dose. Food delayed t_{max} from 1.4 hr. to 2.7 hr compared to fasting.

Importantly, there is clear evidence from trials with other cholinesterase inhibitors, that C_{max} is related to the severity of adverse events, and that a total daily dose spread into smaller individual doses has been an effective way of reducing the potential for adverse effects (9). Slow dose titration (10) and administering medications with food have also been important in reducing the potential for adverse events. In the current study, each participant in the phenserine arm will be titrated at 2-weekly intervals from 5 mg twice-daily to up to 10 mg 3-times daily, if tolerated. The rationale for this 45% AChEI is based on the results from several research groups that have

aimed to quantify the association between the level of cholinesterase inhibition achieved by donepezil and other ChEIs and clinical response. One of the most active group, prof Nordberg's group at Karolinska Institute, reported (11) that " the optimal CSF AChE inhibition for donepezil was over 45% ". This was related to cognitive response. Participants will also be instructed to take each dose with food.

No depressions of any blood cell lines were noted in animal toxicology studies. However, the clinical effects of phenserine on complete blood count (CBC) counts have not been reported in the literature. Nevertheless, a similar molecule based on physostigmine, heptylphysostigmine, was found to induce granulocytopenia in two studies that resulted in the suspension of further clinical trials (12).

In summary, the previous studies have shown acceptable tolerability of 15mg BID, eg Winblad et al(3) (255 patients) showed withdrawals due to side-effects in 15mg BID (5.9%) similar to that of placebo (6.1%). In Kadir et al 2008(13), including 20 patients for 3 months followed by 9M open-label, phenserine 15mgx2, ChEI-related gastrointestinal symptoms were observed in three patients, which resolved in two patients after dose reduction to 20mg/d. This is similar rates as reported for licensed doses of cholinesterase inhibitors. Thus, our interpretation is that 30mg is well tolerated.

Several steps have been taken to ensure safety and tolerability, including a) slow stepwise titration, b) divide the daily dose into three doses eg highest single dose is still 10mg, which reduces Cmax which is the main driver of side-effects, c) ensure IMP is taken with food, and d) frequent in-clinic visit with physical examination and safety laboratory measurements. Any participant who escalates to the highest allowed dose and subsequently experiences intolerable adverse effects will be down titrated to their prior dose level. If more than 2 participants experience dose-limiting side effects at the 10 mg tds dose level, no additional participants will be allowed to dose escalate to that level, and the highest dose that all subsequent participants will be allowed to reach is 10 mg bd.

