1.1. Synopsis

Protocol Title:

A phase 1b dose range finding study of Phenserine compared to Donepezil in participants with early or mild Alzheimer's disease.

Brief Title: Phenserine on the Alzheimer's Treatment Horizon, Study 1

Participants will be randomized into two groups: one group will receive phenserine, and the other will receive donepezil. The phenserine group will begin with a dosage of 5 mg twice daily, with the dose being gradually increased every two weeks as tolerated until the maximum dose of 10 mg three times daily is reached. The donepezil group will start at 5 mg once daily, with the possibility of escalation to 10 mg once daily at Week 4, again aiming for a 45% cholinesterase inhibition as tolerated.

The study is designed to last 8 weeks, with a planned total enrollment of 16 individuals from various centers across Norway. Participants will return for follow-up visits every two weeks, during which pharmacodynamic, pharmacokinetic, and safety assessments will be conducted. The final safety follow-up will occur after the completion of dosing for those who complete the study. Early termination visits will include a comprehensive safety follow-up for those who discontinue the study prematurely.

The primary objective of this study is to assess the effects of phenserine compared to donepezil on exosome biomarkers of cell death in individuals with early or mild AD. Additionally, the study aims to evaluate the safety and tolerability profile of phenserine at ascending doses up to 10 mg three times daily (TDS) in comparison to donepezil at doses up to 10 mg once daily (OD). Furthermore, the study aims to analyze steady-state blood levels of phenserine to characterize and compare dose-response relationships for pharmacodynamic outcomes and key safety assessments. Finally, the study will explore changes in specific biomarkers of Alzheimer's Disease (AD) in cerebrospinal fluid (CSF) and blood plasma, as well as assess phenserine's potential short-term effects on cognition using the FLAME Memory Composite and other cognitive sub-tests.

Participants will be enrolled at six centers across Norway. The study will also be supported by the PROTECT platform, which allows for the recruitment of individuals over 50 years of age who have demonstrated cognitive decline, making them suitable candidates for this study.

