6.6. Dose Modification

As shown in the Study Schema (Figure 1), participants randomized to the phenserine arm will initiate dosing at 5 mg bd and maintain this dose for the first two weeks of study treatment. At the Week 3 visit, participants may be escalated to 10 mg bd, then 10mg tds (Figure 1), based on tolerability, including adverse events, clinical assessment, ECG and safety laboratory measurements. Participants who are unable to tolerate a higher dose will have their dose reduced to the next previous dose level and maintained at that dose through the remainder of the study. This clinical decision will be made by the study physician and the study team at each centre at the visit, or when any safety laboratory results are received during the days after the visit. If needed, the medical monitor and the PI will be contacted. All participants are expected to be at their individualized maintenance dose for 4 weeks (beginning of Week 5 through the end of Week 8).

Participants randomized to the donepezil arm, will initiate dosing at 5 mg od and will be evaluated at the Week 4 visit for dose escalation to 10 mg once daily. For participants in the phenserine arm, dosing will follow a stepwise escalation to ensure safety and efficacy:

- **Weeks 1-2:** Participants will begin with 5 mg twice daily (bd).
- **Weeks 3-4:** Participants will escalate to 10 mg twice daily (bd) if the initial dose is well tolerated.
- **Weeks 5-8:** Participants will further escalate to 10 mg three times daily (tds) based on continued tolerability.

Before any dose escalation, the dosage will be reassessed based on tolerability. If necessary, participants may be required to return to the center for a dose reduction. Throughout the study, dose adjustments will be made according to tolerability. Should any dose escalation lead to adverse effects that compromise the participant's well-being or safety, the dose will be reduced to the previously well-tolerated level. Participants will then continue at this adjusted dose for the remainder of the study period. These procedures are outlined in more detail in the dedicated SOP.

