9.18. Pharmacokinetics

- Plasma PK samples will be collected at W 2, 4, 6, and 8 visits for all IMP participants. Samples will be analyzed for phenserine to determine C_{max} and t_{1/2}. Available data will be analyzed by the DSMB to assess the safety of ongoing patients. PK samples will also be collected at the Week 8 visit, at peak dose, from all other patients (and at the final maintenance dose level for those who down-titrate due to tolerability) prior to taking the

morning dose, to establish steady-state concentration and stored for later analyses aimed at exploring the relationship between exposure and tolerability/efficacy outcomes.

- Instructions for the collection and handling of biological samples will be provided by the sponsor. The actual date and time (24-hour clock time) of each sample will be recorded. Samples will be used to evaluate the pharmacokinetics (PK) of phenserine. Each sample will be divided into aliquots as described in the SOP. These samples may also be used to evaluate safety or efficacy aspects related to concerns arising during or after the study.

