8.2 Pharmacokinetics

- Summary of plasma concentrations at steady state
- PK parameters (C_{max}, T_{max}, AUC if derivable)
- Graphical exposure–response plots versus:
 - AChE inhibition
 - Key exosome markers

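### The Week 8 phenserine level assigned to exposure versus tolerability is, for participants who stepped down, a result of the intolerance, and biases the relation toward zero or the opposite sign

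*Protocol*

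**What the plan says.** The Synopsis sets an aim to "analyze steady-state blood levels of phenserine to characterize and compare dose-response relationships for pharmacodynamic outcomes and key safety assessments". Protocol section 3 and Table 2 repeat it as a secondary objective without naming a visit.

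Protocol 9.18 is the only place that ties particular samples to tolerability. It describes Week 8 samples drawn before the morning dose, at the peak dose "and at the final maintenance dose level for those who down-titrate due to tolerability". Their purpose is "to establish steady-state concentration and stored for later analyses aimed at exploring the relationship between exposure and tolerability/efficacy outcomes". The same section, and the Schedule of Activities, also collect PK samples at Weeks 2, 4, 6 and 8. For that series 9.18 names peak concentration, half-life and DSMB safety review, and it allows use for safety or efficacy questions that arise later.

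On dosing, 2.3.1 states: "Any participant who escalates to the highest allowed dose and subsequently experiences intolerable adverse effects will be down titrated to their prior dose level". Under 6.6, those for whom a step up proves intolerable "will have their dose reduced to the next previous dose level and maintained at that dose through the remainder of the study". Section 2.3.1 also has a cap: once more than 2 participants have dose-limiting effects at 10 mg tds, later participants go no higher than 10 mg bd.

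SAP 8.2 plans "Graphical exposure–response plots versus" two things only, AChE inhibition and key exosome markers. SAP 8.1 summarizes safety by arm and lists dose reductions. Protocol 10.3 promises safety summaries by arm and by dose level. Neither document says which visit or dose supplies the exposure of a participant who stepped down.

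**The concern.** An exposure-tolerability analysis needs the exposure that came before the event. Here the event triggers a dose cut, the cut lasts to Week 8, and the sample named for the analysis is drawn after it. Intolerant participants then carry the level of 10 mg bd, while those who tolerated the top step carry the level of 10 mg tds.

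The trial is meant to inform a Phase 2 dose range. Protocol 2.3.1 itself treats peak exposure as the main driver of side-effects, so a true positive relation is what the sponsor expects. Read from Week 8 levels, that relation would look weaker than it is, absent, or reversed.

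**Working it through.** The documents give no figure on this point, so there is none to reproduce.

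**Inputs from the protocol.** Half-life 6.53 h (2.3.1); dosing intervals 8 h for tds and 12 h for bd (4.4.1); 10 mg per dose in both regimens (Table 3); 12 phenserine participants (1.2); the cap rule (2.3.1).

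**Step 1: shift caused by the dose cut.** One compartment, steady state, k = ln 2 / 6.53 = 0.106 per hour.

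- Trough is proportional to e^(-kτ) / (1 - e^(-kτ)). For bd: 0.280 / 0.720 = 0.388. For tds: 0.428 / 0.572 = 0.748. Ratio bd/tds = **0.52**. For half-lives of 4 to 8.25 h it is 0.43 to 0.55.
- Average level: 20 mg/day over 30 mg/day = **0.67**.
- Peak, treating each dose as a bolus: 1 / (1 - e^(-kτ)). Ratio = 0.572 / 0.720 = **0.79**.

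Section 9.18 specifies a pre-dose sample, so the trough figure is the one closest to the text.

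**Step 2: effect on the comparison.** Simulation of 12 phenserine participants, 4,000 trials per setting. The following are assumptions:

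- between-person CV of exposure 30%, 50% or 80%;
- odds of intolerance at 10 mg tds multiplied by 2, 4 or 8 per doubling of exposure;
- intolerance in 10% or 25% (2.3.1 reports nausea in 19% at 15 mg bd as a rough guide);
- log measurement error SD 0.15;
- everyone reaches 10 mg tds unless capped, and every intolerant participant is recorded at 10 mg bd at Week 8.

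Ratios are geometric means, intolerant over tolerant. Wrong sign means a ratio below 1, among trials with at least one intolerant participant.

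| CV | True ratio on tds | Week 8 trough ratio | Wrong sign, trough, no cap | Wrong sign, trough, with cap | Wrong sign, average level, no cap | Wrong sign, Week 4 common dose, trough, no cap |
|---|---|---|---|---|---|---|
| 30% | 1.09-1.27 | 0.57-0.66 | 93-99% | 81-96% | 73-91% | 15-40% |
| 50% | 1.24-1.73 | 0.65-0.90 | 61-89% | 50-82% | 34-72% | 5-31% |
| 80% | 1.58-2.80 | 0.82-1.46 | 23-66% | 19-58% | 10-46% | 2-24% |

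The true-ratio and Week 8 columns are without the cap. For the peak, multiplying the true ratios by 0.79 gives 0.86-1.00, 0.98-1.37 and 1.25-2.21.

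**Step 3: reading the table.** Without the cap, the Week 8 ratio is divided by 1.92 (trough) or 1.5 (average) in every setting. The cap weakens the shift, because participants held at 10 mg bd have low exposure without having failed tds. The Week 4 common-dose comparison restores the true direction on average (ratios 1.08-1.27, 1.24-1.73 and 1.58-2.81). Its remaining wrong signs are small-sample chance.

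**Step 4: the comparator matters too.** With the cap, using each person's own dose (dose at event for the affected, dose reached for the others) overshoots. At CV 50%, odds ratio 2 and 25% intolerance, the true ratio of 1.22 is recorded as 1.45. Affected and unaffected participants must be evaluated at the same dose.

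**The case against.** The strongest reply is that the documents never prescribe a Week 8-only analysis. PK is sampled at Weeks 2, 4, 6 and 8, the SAP outcome table (4.5) gives Weeks 2-8 for PK, the objective names no visit, and the SAP plans no exposure-tolerability analysis at all. This stands in part: the data for a sound analysis will exist. But the one sentence that assigns samples to tolerability names Week 8 at the reduced dose, and nothing in the SAP replaces it. Nor is Week 6 a safe substitute, since a participant who steps down soon after the Week 4 visit may have no sample on tds.

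A second reply is that intolerance will be visible anyway, through the dose-level safety summaries in protocol 10.3, the dose reductions in SAP 8.1 and the cap rule. This is fair. A reader might infer that the bias would by itself lead Phase 2 to a higher dose; the documents do not support that, because these other sources would show the problem directly. They do not, however, answer the exposure question that the objective poses.

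A third reply concerns size. A reader might infer that the relation will invert by construction. It need not. The CV and the steepness of the relation are not in the documents, the cap softens the effect, and the shift in peak level is much smaller than in trough.

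**Conclusion.** The point holds as a bias of known direction and unknown final size. Following 9.18, a participant stepped down from 10 mg tds is recorded at about 0.52 of the tds trough, 0.67 of the average or about 0.79 of the peak. These figures rest on one-compartment, dose-proportional kinetics and the 6.53 h half-life. A true positive exposure-tolerability relation is therefore attenuated. A change of sign is usual on trough at CV 30%, likely in most settings at CV 50%, and not the rule at CV 80% with a steep relation. No single inversion rate can be stated. The defect lies in the sample assignment in 9.18 and the missing method in SAP 8.2. The down-titration rule is not at fault as a safety measure, and nothing here bears on it. The matter should be settled before the analysis, since the cost is small.

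**What to change.** Change analysis wording only, in protocol 9.18 and SAP 8.2:

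- State that Week 8 levels of participants who stepped down are not used as their exposure for tolerability.
- For tolerability at the top step, compare affected and unaffected participants on exposure at a common dose before that step: the Week 4 sample on 10 mg bd, taking account of the recorded time since the last dose. Count as unaffected only those who took 10 mg tds, so that capped participants are not treated as having tolerated it.
- As a sensitivity analysis, compare predicted exposure at the dose in force at event onset, with unaffected participants evaluated at that same dose.
- Add these exposure-safety plots to the SAP 8.2 list (for example cholinergic adverse events, heart rate and QTc), and summarize safety by dose at onset, in line with protocol 10.3.

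The cost is a few sentences and plots from samples and event dates already collected. There are two limitations to state. The text does not standardize the timing of the Week 4 sample relative to dose. Scaling between regimens assumes dose proportionality, which protocol 2.3.1 puts in doubt by reporting that AUC rose only about 25% over a 4-fold dose increase.
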